7.5 Baseline Data

Demographics

Patient demographics including age, gender, height, weight and body mass index (BMI) will be summarised by treatment group and overall.

Medical History

Relevant medical history (presence/absence of relevant medical conditions), mobility, diabetes status, and type of diabetes will be summarised by treatment group and overall..

Reference Wound Details

Details of the Ulcer type (Pressure Ulcer, Diabetic Foot Ulcer, Venus Leg Ulcer), NPUAP stage (if PU), Wagner Grade (if DFU), Ankle Brachial Pressure Index (if DFU or VLU) Ulcer duration, Ulcer location, whether the wound was debrided at the visit, whether any specific tests related to ulcer performed at the visit and if so what they were, will all be summarised at Baseline by treatment group and overall.

CONFIDENTIAL AND PROPRIETARY

This document contains information that is confidential and proprietary to Smith & Nephew PLC and Smith & Nephew, Inc. and is intended for use only by Smith & Nephew and its manufacturer. It shall not be reproduced or copied in whole or in part, nor shall the contents be disclosed by any means without prior written permission from Smith & Nephew, nor shall anyone make any use of it that is contrary to the expressed or implied wishes of Smith & Nephew

Statistical Analysis Plan	
A Pilot Randomized Controlled Trial to Evaluate an Advanced Borderless Dressing (ALLEVYN™ LIFE Non-Bordered) in the Treatment of Chronic Ulcers	Number: CT1603ALF ST: 1005 Version: 1.0, 27-Jul-2018 Page: 19 of 27

7.6 Disposition Data

The numbers of subjects that are screened, the number of subjects that enter the study and the number of subjects that attend each study visit will be summarised by treatment group and overall.

The reasons for study completion and withdrawal will be summarised by treatment group and overall. The study duration will be summarised by treatment group and overall.

Details of the dates that the first subject was screened, first subject enrolled and the last patient completed will be provided.

7.7 Protocol Deviations

The frequency of protocol deviations and frequency of subjects experiencing each deviation type will summarised by treatment group and overall. This will be done separately for significant deviations, non-significant deviations and all deviations.

7.8 Multiplicity

No adjustments for multiplicity are planned for this study as the study is a pilot with the aim of only collecting data for post-market surveillance and to assist with planning future research.

7.9 Analysis of Primary Endpoint

The primary objective of the study is to compare Health Related Quality of Life (HRQoL) in subjects with chronic wounds. The primary efficacy variable used to measure this objective will be the change from baseline in the CWIS-PSDL scale, over a six week treatment period.

The CWIS-PSDL scale is a 24 item questionnaire split into uses a 5 category Likert scale to answer each item with a 1 - 5 score assigned to each category. The first 12 items focus on whether the subject has experienced any of the items over the past 7 days [Not at all/Not applicable – 5, Seldom – 4, Sometimes – 3, Frequently – 2, Always – 1]. The

CONFIDENTIAL AND PROPRIETARY

This document contains information that is confidential and proprietary to Smith & Nephew PLC and Smith & Nephew, Inc. and is intended for use only by Smith & Nephew and its manufacturer. It shall not be reproduced or copied in whole or in part, nor shall the contents be disclosed by any means without prior written permission from Smith & Nephew, nor shall anyone make any use of it that is contrary to the expressed or implied wishes of Smith & Nephew

Statistical Analysis Plan	 Number: CT1603ALF ST: 1005 Version: 1.0, 27-Jul-2018 Page: 20 of 27
A Pilot Randomized Controlled Trial to Evaluate an Advanced Borderless Dressing (ALLEVYN™ LIFE Non-Bordered) in the Treatment of Chronic Ulcers	

last 12 items focus on how stressful the experience of the items has been over the past 7 days [Not at all/Not applicable – 5, Slightly – 4, Moderately – 3, Quite a bit – 2, Very applicable – 1]. These scores are then transformed into a 0-100 scale at each time point, where a high score represents a 'good' HRQoL and a low score represents a 'poor' HRQoL, using the following formula:

$$PSDL\ Score = \frac{\text{Sum of item scores} - 24}{96} \times 100$$

The increase in CWIS-PSDL score between baseline and 6 weeks will be derived as follows:

$$PSDL\ score\ increase = (Score\ at\ 6\ weeks - Score\ at\ baseline)$$

Subject responses to individual items at each assessment will be summarized using counts and percentages, by treatment (and overall), wound type and amount of exudate at baseline.

The CWIS-PSDL score at Baseline and 6 weeks will be summarized as a continuous variable by treatment, wound type (and overall) and level of exudate at baseline.

The increase in CWIS-PSDL score between the Baseline and 6 weeks will be summarized as a continuous variable by treatment, wound type (and overall), baseline mobility and level of exudate at baseline.

Primary Analysis of Primary Endpoint

For the primary analysis an ANCOVA model will be fit to the FAS population with the increase in CWIS-PSDL score between Baseline and 6 weeks as the dependent variable. The model will contain a term for treatment (ALNB or SC) and the following terms will be added to the model using a stepwise selection procedure with an F-value to attain a significance level of 0.1: centre, wound type and BMI, baseline CWIS-PSDL score.

The null hypothesis will be that there is no difference between the treatments in terms of the increase from baseline to 6 weeks in CWIS-PSDL score. An estimate of the LS mean

CONFIDENTIAL AND PROPRIETARY

This document contains information that is confidential and proprietary to Smith & Nephew PLC and Smith & Nephew, Inc. and is intended for use only by Smith & Nephew and its manufacturer. It shall not be reproduced or copied in whole or in part, nor shall the contents be disclosed by any means without prior written permission from Smith & Nephew, nor shall anyone make any use of it that is contrary to the expressed or implied wishes of Smith & Nephew

Statistical Analysis Plan	 Number: CT1603ALF ST: 1005 Version: 1.0, 27-Jul-2018 Page: 21 of 27
A Pilot Randomized Controlled Trial to Evaluate an Advanced Borderless Dressing (ALLEVYN™ LIFE Non-Bordered) in the Treatment of Chronic Ulcers	

difference between the treatments (ALNB – SC) for the CWIS-PSDL score will be reported, along with the corresponding 95% confidence interval and p-value.

If the assumptions of ANCOVA are not met then a non-parametric analysis will be considered the primary analysis for this variable. The same analysis will be done as for the parametric analysis however a Rank ANCOVA model will be used instead.

Secondary Analysis of Primary Endpoint

If the data meets the assumptions of using ANCOVA then as a secondary analysis a repeated measures ANCOVA model will be used, with the CWIS-PSDL score as the dependent variable. As a minimum the model will contain terms for treatment, visit and treatment-by-visit interaction. The following terms will be added to the model using a stepwise selection procedure with an F-value to attain a significance level of 0.1: centre, wound type, BMI and baseline CWIS-PSDL score.. P-values for the type III effects in the model will be presented.

Sensitivity Analysis

If LOCF methods are used to account for any missing CWIS-PSDL data at 6 weeks then a sensitivity analysis the same as the primary analysis (ANCOVA model) described above will be carried out on the data treating all missing data as missing with no imputation.

The primary endpoint analysis will be repeated using the per-protocol population (with and without the LOCF imputation).

CONFIDENTIAL AND PROPRIETARY

This document contains information that is confidential and proprietary to Smith & Nephew PLC and Smith & Nephew, Inc. and is intended for use only by Smith & Nephew and its manufacturer. It shall not be reproduced or copied in whole or in part, nor shall the contents be disclosed by any means without prior written permission from Smith & Nephew, nor shall anyone make any use of it that is contrary to the expressed or implied wishes of Smith & Nephew

Statistical Analysis Plan	
A Pilot Randomized Controlled Trial to Evaluate an Advanced Borderless Dressing (ALLEVYN™ LIFE Non-Bordered) in the Treatment of Chronic Ulcers	Number: CT1603ALF
	ST: 1005
	Version: 1.0, 27-Jul-2018
	Page: 22 of 27

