## 10.2 EFFICACY

### 10.2.1 Primary Efficacy

The primary objective of the study is to compare HRQoL in subjects with chronic wounds. The primary efficacy variable used to measure this objective will be the change from baseline in the CWIS-PSDL scale, over a six week treatment period.

The CWIS-PSDL scale is a 24 item questionnaire split into uses a 5 category Likert scale to answer each item with a 1 - 5 score assigned to each category. The first 12 items focus on whether the subject has experienced any of the items over the past 7 days [Not at all/Not applicable – 5, Seldom – 4, Sometimes – 3, Frequently – 2, Always – 1]. The last 12 items focus on how stressful the experience of the items has been over the past 7 days [Not at all/Not applicable – 5, Slightly – 4, Moderately – 3, Quite a bit – 2, Very applicable – 1]. These scores are then transformed into a 0-100 scale at each time point, where a high score represents a 'good' HRQoL and a low score represents a 'poor' HRQoL, using the following formula:

$$PSDL\ Score = \frac{Sum\ of\ item\ scores - 24}{96} \times 100$$

The increase in CWIS-PSDL score between baseline and 6 weeks will be derived as follows:

$$\text{PSDL score increase} = (\text{Score at 6 weeks} - \text{Score at baseline})$$

Subject responses to individual items at each assessment will be summarized as ordinal variables by treatment, wound type (and overall) and level of exudate at baseline.

The CWIS-PSDL score at Baseline and 6 weeks will be summarized as a continuous variable by treatment, wound type (and overall) and level of exudate at baseline.

The increase in CWIS-PSDL score between the Baseline and 6 weeks will be summarized as a continuous variable by treatment, wound type (and overall), baseline mobility, and level of exudate at baseline.

For the primary analysis, an ANCOVA model will be fit to the FAS population with the increase in CWIS-PSDL score between the Baseline and 6 weeks as the dependent variable, treatment (ALNB or SC) and center will be included in the model as fixed effects and subject will be included as a random effect. The covariates for the model to be considered will be wound type, baseline CWIS-PSDL score, baseline exudate level, baseline mobility, and baseline wound area.

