The null hypothesis will be that there is no difference between the treatments in the increase from baseline to 6 weeks in the CWIS-PSDL score. An estimate of the LS mean difference between the treatments (ALNB – SC) for the CWIS-PSDL score will be reported, along with the corresponding 95% confidence interval and p-value.

If the assumptions of ANCOVA are not met then a non-parametric analysis will be considered the primary analysis for this variable. A Wilcoxon Rank-Sum test will be used to test for a difference in the increase from baseline score between the two treatments and the Hodges-Lehmann estimate of the median difference will be reported with the corresponding 95% confidence interval.

This analysis will be repeated using the per-protocol population and used as supportive evidence to the primary analysis. Any further sensitivity analyses and discussion of methods of handling missing data will be defined in the SAP.

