6.2 Randomisation

Subjects will be randomly assigned in a 5:3 ratio of ALNB:SC. Subjects will be stratified by ulcer type (PU, DFU, LU).

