7.10 Analysis of Key Secondary Endpoints

Health-related quality of life (HRQoL)

The increase in CWIS-PSDL scale scores from baseline to three and twelve weeks (separately) will be analysed in the same way as described in the primary endpoint analysis.

Increase from baseline scores to three, six, and twelve weeks will be calculated and analysed separately in the same way as described in the primary endpoint analysis for the following variables also:

- CWIS-SL scale
- CWIS-WB scale
- CWIS-GQ scale
- CWIS-SQ scale

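### The primary ANCOVA chooses every covariate by stepwise selection at 0.1, so its confidence interval is modestly too narrow, and no fixed-covariate analysis backs it up

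*SAP*

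**What the plan says.** **SAP 7.9, primary analysis.** Treatment is the only guaranteed term. The rest are added by a "stepwise selection procedure with an F-value to attain a significance level of 0.1: centre, wound type and BMI, baseline CWIS-PSDL score". The LS mean difference (ALNB minus SC) is reported with a 95% interval and p-value; nothing is said about allowing for the selection.

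**SAP 7.9, fallback.** If the ANCOVA assumptions fail: "The same analysis will be done as for the parametric analysis however a Rank ANCOVA model will be used instead".

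**SAP 7.9, supporting analyses.** If LOCF was used at week 6, "a sensitivity analysis the same as the primary analysis (ANCOVA model) described above will be carried out" without imputation. The per-protocol analyses repeat the primary one. The repeated-measures model fixes treatment, visit and their interaction, and selects the same four candidates at the same level.

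**SAP 7.10.** The other CWIS scales and visits are "analysed separately in the same way as described in the primary endpoint analysis".

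**Protocol 10.2.1.** Here "treatment (ALNB or SC) and center will be included in the model as fixed effects", with subject as a random effect. For the rest: "The covariates for the model to be considered will be wound type, baseline CWIS-PSDL score, baseline exudate level, baseline mobility, and baseline wound area". The fallback is a Wilcoxon rank-sum test, and "the Hodges-Lehmann estimate of the median difference will be reported with the corresponding 95% confidence interval".

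**SAP 6.2** stratifies randomisation by ulcer type.

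**The concern.** Selecting covariates on the outcome data and then computing an ordinary interval from the chosen model has two effects. Terms that happen to lower the residual variance are kept, and the standard error ignores the fact that another sample would have produced another model. Both make the interval too narrow.

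The selection is also repeated for each scale, visit and population. A difference between weeks 3, 6 and 12, or between the full analysis set and the per-protocol set, may then partly reflect a different adjustment rather than a different effect.

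At stake is the pilot's main product. Protocol 8.2 says the study should supply an effect-size estimate for planning a full-scale trial. No analysis with a fixed covariate set is planned against which the selected model could be judged.

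**Working it through.** **1. Inputs from the documents.** Allocation 5:3 with 25 ALNB subjects (SAP 6.1); three ulcer-type strata (SAP 6.2); up to 6 centres (Protocol synopsis); two-sided 5% tests and 95% intervals (SAP 7.1); four candidates at level 0.1 (SAP 7.9).

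**2. The plan's own figure.** 25 × 8/5 = 40, which agrees with the stated total. No power, SD or effect size is given, so there is no precision figure to reproduce.

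**3. Number of selected models.** PSDL at 3 visits plus 4 other scales at 3 visits: 3 + 12 = 15. One is the primary analysis and 14 fall under SAP 7.10.

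**4. Simulation.** Assumed: no treatment effect; blocks of 8 within wound types of 16/16/8; 6 balanced centres; baseline/week-6 correlation r of 0.5-0.8; wound-type shift of 0 or 0.4 SD between adjacent types; centre effects of 0 or up to ±0.4 SD; 0.1 used both to enter and to stay (the SAP gives one level). There were 10,000 runs per scenario. Model (a) is treatment + baseline + wound type. Model (b) is (a) plus fixed centre. The SD is the true SD of the treatment estimate, in SDs of the CWIS score.

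| r, wound shift, centre effect | Error %: stepwise / (a) / (b) | SD: stepwise / (a) / (b) |
|---|---|---|
| 0.5, 0, 0 | 6.0 / 5.3 / 5.2 | 0.296 / 0.288 / 0.314 |
| 0.7, 0, 0 | 6.1 / 4.9 / 5.2 | 0.245 / 0.236 / 0.257 |
| 0.7, 0.4, 0 | 6.1 / 5.3 / 5.5 | 0.247 / 0.239 / 0.260 |
| 0.8, 0, 0 | 6.4 / 5.1 / 5.1 | 0.206 / 0.199 / 0.216 |
| 0.7, 0, 0.4 | 6.9 / 5.0 / 5.1 | 0.263 / 0.254 / 0.257 |
| 0.5, 0.4, 0.4 | 6.4 / 4.9 / 5.1 | 0.313 / 0.300 / 0.312 |

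Simulation error on the error rates is about ±0.5 points. Coverage is 100 minus the error: 93.1-94.0% for stepwise and 94.7-95.1% for (a).

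Plausibility check on (a) with no wound or centre effect: SD ≈ √(1 − r²) × √(1/25 + 1/15) = √(1 − r²) × 0.327. This gives 0.283, 0.233 and 0.196 for r = 0.5, 0.7 and 0.8, just below the simulated 0.288, 0.236 and 0.199.

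**5. Reading the results.**
- Shortfall of the reported standard error, 1 − (mean SE / true SD): stepwise 5.0-8.0%, (a) 0.4-1.6%, (b) 1.1-2.4%.
- Stepwise against (a): true SD 2.6-4.2% larger (for example 0.245/0.236 = 1.038), yet the interval is 0.6-4.1% narrower.
- Stepwise against (b): SD 4.3-5.9% smaller when centre has no effect (0.245/0.257 = 0.953) and 0.2-2.3% larger when it has one (0.263/0.257 = 1.023). Stepwise is not noisier in general.
- Baseline is dropped in 5-8% of runs at r = 0.5, 21-25% at 0.7 and 38% at 0.8. The slope of change on baseline is r − 1, so it weakens as r rises, and so does the gain from adjusting: the variance ratio is (1 + r)/2, or 0.75, 0.85 and 0.90.
- Wound type is dropped in 29-47% of runs when it matters and 89-90% when it does not.
- The selected set differs between weeks 6 and 12 in 37-55% of runs (residual correlation between visits assumed 0.7).

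**6. Second simulation.** A separate program used nine scenarios of 6,000 runs, with different effect sizes, 3 or 6 centres, and one case at N = 34. Stepwise error was 5.5-7.3% against 4.6-5.5% for (a). The standard-error shortfall was about 1-8%. The mildest case had strong covariates that were almost always selected (5.5%); the worst was N = 34 with 6 centres (7.3%). Smaller repeats of the first simulation (2,000 to 4,000 runs per scenario, hence noisier) gave 5.7-7.5% against 4.5-6.5%.

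**7. Protocol 10.2.1 against SAP 7.9.**
- Centre: fixed term, now optional.
- Random subject effect: present, now absent.
- Exudate, mobility and wound area: covariates to consider, now absent.
- BMI: not mentioned, now a candidate.
- Fallback: Wilcoxon with a Hodges-Lehmann interval, now rank ANCOVA, whose treatment difference is in rank units.

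SAP 7.15 lists two changes, one on the Bates-Jensen comparison and one on the confidence limit for serious device-related events. None of the five above appears.

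**The case against.** **It is a pilot.** There is no power claim and no multiplicity control, and Protocol 5.6 expects too little data for significance. One or two points of extra error change no planned decision. A 5-8% shortfall in the standard error also sits beside run-to-run variation of about 12% in the reported standard error at N = 40, even with a fixed model. This stands as a limit on severity. But the shortfall is systematic, and estimation is the stated purpose.

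**Switching sets seldom moves the estimate much.** In repeat runs the stepwise and fixed week-6 estimates correlated 0.91-0.97, with a median gap of 0.01-0.11 standard errors. The 90th percentile was 0.32-0.44 without centre effects and 0.68-0.75 with them. So the comparability problem is usually small and becomes noticeable mainly if centres differ, which the documents cannot tell us.

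**The procedure is prespecified, and the protocol left covariates open.** Candidates, test and level are indeed named, so this is not an analyst's free choice. Dropping covariates that were only to be considered is weak evidence of a departure. Centre and the fallback, however, were firm commitments, and prespecifying the selection does not correct the interval.

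**The new fallback has merit.** Rank ANCOVA can adjust, which the Wilcoxon test cannot. Arm-level summaries in CWIS points also remain. What is lost is the between-group interval in those points, and only if the ANCOVA assumptions fail.

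**Conclusion.** The concern holds and should be fixed, though the harm is modest. The adjustment set depends on the data, no planned between-group analysis of the CWIS endpoints fixes it, and the nominal 95% interval covers roughly 93-94.5% across the two main simulations. The true SD of the estimate is a few per cent larger than under a short fixed model, while the reported interval is slightly narrower. All magnitudes depend on assumed correlations, covariate effects, stratum sizes and centre balance, so they should be read as ranges. The absence of a fixed-covariate analysis and the omissions from SAP 7.15 follow from the text alone and need no assumption.

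**What to change.** 1. In SAP 7.9 and 7.10, always include treatment, wound type and the baseline score of the scale being analysed, for every scale, visit and population, and in the repeated-measures model. This also settles which baseline score the SL, WB, GQ and SQ models use.
2. State how centre is handled. With 6 sites it costs 6 − 1 = 5 degrees of freedom and, if centre has no effect, about 9% in SD (0.314/0.288 = 1.090). One workable choice is to leave it out of the primary model and run the protocol's fixed-centre model as a sensitivity analysis. This is a judgement for the sponsor.
3. Keep any stepwise model as a sensitivity analysis only.
4. If the rank ANCOVA is used, also report the Hodges-Lehmann difference with its 95% interval in CWIS points.
5. Record in SAP 7.15, with reasons: the centre decision, the removed random subject effect (not separable from residual error with one change score per subject), BMI, the dropped exudate, mobility and wound-area covariates, and the changed fallback.

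Cost: SAP wording, plus 1 + 2 = 3 degrees of freedom for baseline and wound type, leaving 40 − 2 − 3 = 35 residual degrees of freedom (30 if centre is also fixed at 6 sites). No additional data are needed.

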#### 10.2.2.1 *Key Secondary*

##### Health-related quality of life (HRQoL)

Subject-reported HRQoL variables (measured using the CWIS) include:

- The increase in CWIS-PSDL scale scores from baseline to three and twelve weeks (separately). This will be analyzed in the same way as described in the primary efficacy analysis.
- Increase from baseline scores to three, six, and twelve weeks will be calculated and analyzed separately in the same way as described in the primary efficacy analysis, for the following variables:
  - CWIS-SL scale
  - CWIS-WB scale
  - CWIS-GQ scale
  - CWIS-SQ scale

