7.1 General

Smith & Nephew's Global Biostatistics group will conduct the statistical analysis for this study. Unless otherwise stated, all significance tests and hypothesis testing will be two-sided, performed at the 5% significance level. Resulting p-values will be quoted and 95% two-sided confidence intervals will be generated where appropriate. All p-values will be

CONFIDENTIAL AND PROPRIETARY

This document contains information that is confidential and proprietary to Smith & Nephew PLC and Smith & Nephew, Inc. and is intended for use only by Smith & Nephew and its manufacturer. It shall not be reproduced or copied in whole or in part, nor shall the contents be disclosed by any means without prior written permission from Smith & Nephew, nor shall anyone make any use of it that is contrary to the expressed or implied wishes of Smith & Nephew

Statistical Analysis Plan	 Number: CT1603ALF ST: 1005 Version: 1.0, 27-Jul-2018 Page: 13 of 27
A Pilot Randomized Controlled Trial to Evaluate an Advanced Borderless Dressing (ALLEVYN™ LIFE Non-Bordered) in the Treatment of Chronic Ulcers	

rounded to three decimal places, p-values less than 0.001 will be presented as ‘<0.001’ in all tables.

Where data summaries are specified, categorical and ordinal variables will be summarized with frequencies and percentages. Continuous variables will be summarized with the following summary statistics: number of observations, mean, median, standard deviation, minimum and maximum values. All analyses will be performed in SAS 9.4 (or later).

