7.15 Changes in Analysis Methods Specified in the Protocol

The following changes were made to the methods specified in the protocol:

- For the Modified Bates- Jensen Wound Assessment Tool, instead of using a t-test to test for a difference between treatments in the total score at 12 weeks, the repeated measures ANOVA model which was already being used will also be used to

CONFIDENTIAL AND PROPRIETARY

This document contains information that is confidential and proprietary to Smith & Nephew PLC and Smith & Nephew, Inc. and is intended for use only by Smith & Nephew and its manufacturer. It shall not be reproduced or copied in whole or in part, nor shall the contents be disclosed by any means without prior written permission from Smith & Nephew, nor shall anyone make any use of it that is contrary to the expressed or implied wishes of Smith & Nephew

Statistical Analysis Plan	 smith&nephew
A Pilot Randomized Controlled Trial to Evaluate an Advanced Borderless Dressing (ALLEVYN™ LIFE Non-Bordered) in the Treatment of Chronic Ulcers	Number: CT1603ALF
	ST: 1005
	Version: 1.0, 27-Jul-2018
	Page: 27 of 27

estimate the difference in least squares mean (LSMean) between treatments at the 12 week visit along with associated 95% confidence interval.

- The number of serious device-related adverse events is expected to be low, so it would not be useful to calculate the 1-sided upper 95% CI as originally planned in the protocol. Instead the number will be summarised and the individual cases will be listed.

CONFIDENTIAL AND PROPRIETARY

This document contains information that is confidential and proprietary to Smith & Nephew PLC and Smith & Nephew, Inc. and is intended for use only by Smith & Nephew and its manufacturer. It shall not be reproduced or copied in whole or in part, nor shall the contents be disclosed by any means without prior written permission from Smith & Nephew, nor shall anyone make any use of it that is contrary to the expressed or implied wishes of Smith & Nephew

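### If ANCOVA assumptions fail, the SAP's rank ANCOVA fallback gives an effect in ranks; no ALNB minus SC difference in scale points is clearly required, and the switch from the protocol is unlisted

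*SAP*

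**What the plan says.** Both documents use the same trigger. In the SAP's words, "If the assumptions of ANCOVA are not met then a non-parametric analysis will be considered the primary analysis for this variable". They differ in what follows.

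- **Protocol 10.2.1** names a Wilcoxon rank-sum test on the increase from baseline and adds that "the Hodges-Lehmann estimate of the median difference will be reported with the corresponding 95% confidence interval". For the key secondary PSDL visits, protocol 10.2.2.1 says "This will be analyzed in the same way as described in the primary efficacy analysis", and it applies the same rule to the other CWIS scales.
- **SAP 7.9** says instead: "The same analysis will be done as for the parametric analysis however a Rank ANCOVA model will be used instead". Hodges-Lehmann is no longer mentioned. The sentence does not say what is ranked, on which scale the difference is reported, or whether it is back-transformed. SAP 7.10 extends the method to the other CWIS scales, which are "analysed separately in the same way as described in the primary endpoint analysis for the following variables also".
- **SAP 7.15** opens with "The following changes were made to the methods specified in the protocol" and gives two entries. One concerns the Bates-Jensen total score and the other the confidence limit for serious device-related adverse events.

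The primary objective (SAP 4.1) is one of estimation. Protocol 8.2 wants an effect size to guide a later full-scale trial.

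**The concern.** The primary result in this branch would be a rank difference with its interval and a p-value. A rank difference does not say how many points of quality of life separate the arms, and that is what the objective asks for and what the planner of a later trial needs. The protocol had named an estimate on the original scale for exactly this case. The SAP drops it without listing the change, so a reader who relies on 7.15 would still expect it.

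The same rule governs the key secondary CWIS analyses: PSDL at 2 visits plus 4 scales at 3 visits, 2 + 4 × 3 = 14. Up to 15 analyses are exposed, each only where its own assumptions fail.

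**Working it through.** **Inputs.** The 5:3 ratio and 25 ALNB subjects are from SAP 6.1. They give 25 × 3/5 = 15 SC subjects and 25 × 8/5 = 40 in total, which matches the plan. The documents give no SD and no distribution for the increase, so every SD and shape below is assumed.

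**1. Is a points estimate required elsewhere in this branch?**

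- Rank ANCOVA (SAP 7.9): difference and CI carried over, in ranks.
- Repeated-measures model (SAP 7.9): not run, because its condition is "If the data meets the assumptions of using ANCOVA then as a secondary analysis a repeated measures ANCOVA model will be used".
- No-imputation sensitivity analysis (SAP 7.9): described as an ANCOVA, but run only if LOCF was used. The text does not say whether it stays parametric in this branch.
- Group summaries: "Continuous variables will be summarized with the following summary statistics: number of observations, mean, median, standard deviation, minimum and maximum values" (SAP 7.1). These are by arm, with no between-arm difference or CI.
- The ordinary ANCOVA LS mean difference may still be shown as a non-primary result. The text neither withdraws it nor requires it in this branch.

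**2. Ranks do not convert to points.** For arms totalling N subjects without ties, the difference in mean ranks is N × (P − 0.5), where P is the probability that a random ALNB increase exceeds a random SC increase. With N = 40 it cannot exceed 20. A difference of 6 gives P = 0.5 + 6/40 = 0.65. The shift that produces P = 0.65, in SD units:

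| Assumed shape | Shift | SD 10 | SD 25 |
|---|---|---|---|
| Normal, √2 × z(0.65) | 0.54 | 5.4 points | 13.6 points |
| t(3), simulated | 0.39 | 3.9 points | 9.7 points |
| Exponential, −ln(0.70) | 0.36 | 3.6 points | 8.9 points |

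A simulation with 25 and 15 subjects, t(3) errors, SD 15 and a true shift of 10 points gave an average Hodges-Lehmann estimate of 9.9 points and a rank ANCOVA difference of 8.9 ranks. Doubling every change score moved Hodges-Lehmann to 19.9 points and left the rank result at 8.9.

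**3. What Hodges-Lehmann gains, and when.** There are 25 × 15 = 375 pairwise differences. The lower 95% limit is near position 375/2 − 1.96 × √(375 × 41/12) = 187.5 − 70.2 = 117. For an equal-variance shift, the mean half-width relative to the pooled t interval is 1.04 (normal), 0.82 (t(3)) and 0.76 (exponential). Put the other way, a t interval rebuilt from arm summaries is 1/0.819 = 1.22 to 1/0.764 = 1.31 times as wide for the two non-normal shapes.

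**4. Where that gain fails.** ANCOVA assumptions also include equal variance. With a true mean difference of zero and the SC spread at 1.5 or 2 times that of ALNB, 95% CI coverage of the mean difference was:

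| Assumed shape | Hodges-Lehmann | Welch, from arm means and SDs |
|---|---|---|
| Normal | about 94% and 92% | about 95% |
| Exponential, mean-centred | about 86% and 79% | about 92% to 94% |

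In the exponential settings the Hodges-Lehmann estimate averaged 0.19 and 0.36 ALNB SDs although the means were equal. It targets the median pairwise difference, which equals the mean effect under a pure shift but not in general.

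**The case against.** The strongest reply is that the SAP does specify an estimate. The sentence before the fallback requires an LS mean difference with 95% CI and p-value, and the fallback says the analysis is otherwise the same. That stands. A reader might infer that no treatment effect is reported at all in this branch, and the text does not support that. What is open is the scale.

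The ordinary ANCOVA result is also never withdrawn; the fallback only changes which analysis counts as primary. The tables, figures and listings shells, which SAP Section 2 names as a related document but which are not among the documents reviewed, could settle the display. This leaves the gap as one of clarity. A primary estimate should not depend on an inference or on a table shell.

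A planner can also compute a points difference from arm means, SDs and numbers. That stands too and limits the harm, but such an interval is unadjusted and not pre-specified.

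Nor is Hodges-Lehmann better in general. A reader might take the 22% to 31% width figure as a general gain, but it holds only for the assumed equal-variance non-normal shifts. With unequal spread the interval can miss the mean difference far too often. Hodges-Lehmann should therefore be neither the only points estimate nor labelled as the mean effect.

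Finally, rank ANCOVA can adjust for wound type and baseline, which the Wilcoxon test cannot. The choice of test is defensible and is not criticised here.

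**Conclusion.** The point holds in a limited form. If ANCOVA assumptions fail, following SAP 7.9 literally gives a primary estimate in ranks, no ALNB minus SC difference with CI in scale points is clearly required, and 7.15 does not record the departure from protocol 10.2.1.

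The method switch and the missing entry are plain from the text. The lack of a points estimate rests on reading rank ANCOVA in its usual sense, with the LS mean difference taken on ranks, and on no unseen shell saying otherwise.

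The size is modest. The branch is conditional, the study is a pilot with no power claim and no multiplicity control, and arm means and SDs are still reported. The point conversions and coverage figures rest on assumed SDs and shapes and show direction and rough scale only. The change is worth making because it is cheap and restores an output the protocol had already named. It does not threaten the validity of the trial.

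**What to change.** Add to SAP 7.9, and apply to each scale in 7.10 in its own points:

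> If ANCOVA assumptions are not met, the Rank ANCOVA gives the primary p-value. Two unranked estimates of ALNB − SC in scale points are reported with 95% CIs, for estimation only: the Hodges-Lehmann estimate (median of pairwise differences, unadjusted, equal to the mean effect only under a pure shift) and the ANCOVA LS mean difference. Neither is a second test.

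Add one entry to 7.15: the Wilcoxon test is replaced by rank ANCOVA, with the reason, and the Hodges-Lehmann estimate is retained.

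**Cost.** A few sentences and a few output lines. No new data are needed, and neither the main model nor the test changes.

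**Downside.** An unadjusted interval stands beside an adjusted test, and the two can disagree. In simulations with 25 and 15 subjects and assumed non-normal errors, they disagreed in about 3% to 7% of trials with no effect. With a 0.5 SD shift the figure was roughly 10% to 37%, depending on the baseline correlation and how the data were generated. For that reason the text must say which result is the test.
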